9.4.2.2.2 Time to Response

Time to response is defined as the time from the date of randomisation (or date of first dose of study treatment, for the biopsy sub-study) until the date of first documented response. The date of first documented response should coincide with that used for the DoR endpoint. Time to response will not be defined for those patients who do not have a documented response.

The TTR will be summarised (ie, number of patients [%] based upon the number of responders for each treatment arm) by the scheduled assessment timepoint that the response was first observed. Additionally, descriptive summary statistics (ie, minimum, maximum, median, Q1 and Q3) will also be presented.

9.4.2.2.3 Progression Free Survival

Progression free survival is defined as the time from the date of randomisation (or date of first dose for the biopsy sub-study) until the date of objective disease progression per RECIST 1.1 as assessed by BICR or death (by any cause in the absence of progression), (ie, date of event or censoring – date of randomisation/the first dose of study treatment + 1). PFS will be analysed using the full analysis set (main study) and the safety analysis set (biopsy sub-study), and will include all patients in the analysis set regardless of whether the patient withdraws from therapy or receives another anti-cancer therapy or clinically progresses prior to RECIST 1.1 progression. Patients who have not progressed or died at the time of analysis will be censored at the time of the latest date of assessment from their last evaluable RECIST assessment. However, if the patient progresses or dies immediately after 2 or more consecutive missed visits, the patient will be censored at the time of the latest evaluable RECIST assessment prior to the 2 missed visits (Note: Not evaluable visit is not considered as missed visit). If the patient has no evaluable visits or does not have baseline data, they will be censored at Day 1 unless they die within 2 visits of baseline (16 weeks plus 1 week allowing for a late assessment within the visit window).

The PFS time will always be derived based on scan/assessment dates and not visit dates.

RECIST 1.1 assessments/scans contributing toward a particular visit may be performed on different dates. The following rules will be applied:

- For investigator assessments, the date of progression will be determined based on the earliest RECIST assessment/scan dates of the component that indicates progression.
- For BICR assessments, the date of progression will be determined based on the earliest dates of the component that triggered the progression on the first set of scans that indicates progression for the adjudicated reviewer selecting disease progression per RECIST 1.1, or of either reviewer where both reviewers select disease progression per RECIST 1.1 as a time point response, and there is no adjudication for central review (BICR) data.
- When censoring a patient for PFS, the patient will be censored at the latest scan dates contributing to a particular overall visit assessment.

Analysis methods:

PFS will be analysed for both BICR and investigator recorded assessment.

Kaplan-Meier plots of PFS will be presented by treatment group. Summaries of the number and percentage of patients experiencing a PFS event and the type of event (RECIST 1.1 or death) will be provided along with median PFS for each treatment. The proportion of patients alive and progression free at 3, 6, 9, and 12 months from randomisation will be summarised by treatment group.

PFS will be analysed using a log rank test stratified by the randomisation stratification factors (baseline LDH and IO resistance). The HR together with its 95% CI and p-value will be presented. The HR and CI will be estimated from a stratified Cox proportional hazards model (with ties = Efron), and the CI will be calculated using a profile likelihood approach. The stratification variables will be defined according to data from the IXRS.

Further sensitivity analyses to explore the robustness of the primary PFS endpoint will be documented in the SAP.

9.4.2.2.4 Overall Survival

The OS is defined as the time from the date of randomisation (or date of first dose for the biopsy sub-study) until death due to any cause regardless of whether the patient withdraws from study treatment or receives another anti-cancer therapy. Any patient not known to have died at the time of analysis will be censored based on the last recorded date on which the patient was known to be alive.

Note: Survival calls will be made following the date of DCO for the analysis (these contacts should generally occur within 7 days of the DCO). If patients are confirmed to be alive or if the death date is after the DCO date, then these patients will be censored at the date of DCO.

OS will be analysed using the same methodology specified for PFS, but with landmark estimates summarised at 6, 9, 12, and 18 months from randomisation.

9.4.2.2.5 Change in Tumour Size

Percentage change from baseline in TL tumour size is based on the RECIST 1.1 TL measurements as assessed by BICR. Tumour size is the sum of the longest diameters of the TLs. The percentage change from baseline in TL tumour size at post-baseline assessment (Week 16) is obtained for each patients taking the difference between the sum of the TLs at post-baseline assessment and the sum of the TLs at baseline divided by the sum of the TLs at baseline times 100.

Patients who progress before week 16 should have had a tumour assessment performed at the time of progression prior to treatment discontinuation. The tumour size from their latest progression assessment will be used instead of the week 16 assessment for these patients. Best percentage change will also be summarised.

Best percentage change

The absolute change and percentage change from baseline in the sum of tumour size at each visit will be calculated. The best change in tumour size (ie, depth of response) is the largest decrease from baseline or the smallest increase from baseline in the absence of a reduction and will include all assessments prior to the earliest of death in the absence of progression, any evidence of progression, the start of subsequent anti-cancer therapy or the last evaluable RECIST assessment if the patient has not died, progressed or started subsequent anti-cancer therapy.

The percentage change in target lesion tumour size from baseline at 16 weeks, and best percentage change in tumour size will be presented visually for each patient by waterfall and spider plots.

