7.1.2 Follow-up of Patients Post Discontinuation of Study Treatment

After study treatment discontinuation, all patients will be followed up for safety assessments 30 days after their last dose of study treatment for ceralasertib monotherapy or 180 days after last dose of study treatment for ceralasertib and durvalumab combination (ie, the safety follow-up visit). Patients will also be followed for survival status and post discontinuation anti-cancer therapies. Additional assessments to be performed at the time of the safety follow-up are detailed in the SoA (Section 1.3). For country-specific requirements for Belgium and France see Appendices K 1.1 and K 1.2, respectively.

Patients who have discontinued study treatment prior to objective RECIST 1.1-defined radiological progression will be followed up with tumour assessments according to the SoA until RECIST 1.1 defined disease progression or death regardless of whether or not the patient started a subsequent anti-cancer therapy, unless they have withdrawn all consent to study related assessments.

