9.4.2 Efficacy

9.4.2.1 Primary Endpoint(s)

9.4.2.1.1 Calculation or Derivation of Tumour Response Variables

9.4.2.1.1.1 Investigator RECIST 1.1-based assessments:

All RECIST 1.1 assessments, whether scheduled or unscheduled, will be included in the calculations. This is also regardless of whether a patient discontinues study treatment or receives another anti-cancer therapy.

At each visit, patients will be programmatically assigned a RECIST 1.1 visit response of CR, PR, stable disease, disease progression, or not evaluable depending on the status of their disease compared with baseline and previous assessments. Baseline will be assessed within the 21 days prior to randomisation (or first dose of study drug for the biopsy sub-study). The tumour response endpoints (ORR, DoR, BOR, TTR, PFS, and change in tumour size) will then be derived from the scan dates and overall visit responses.

9.4.2.1.1.2 BICR (Main study only):

A BICR of radiological scans will be performed on all patients in the main study to confirm the robustness of the investigator-assessed ORR, DoR, BOR, TTR, PFS, and change in tumour size endpoints.

All images will be collected centrally. The imaging scans will be reviewed by 2 independent radiologists using RECIST 1.1 and will be adjudicated, if required. For each patient, the BICR will define the overall visit response data (CR, PR, stable disease, disease progression, or not evaluable) and the relevant scan dates for each time point (ie, for visits where response or progression is/is not identified). Patients who have RECIST 1.1-defined disease progression on study treatment based on progression of non-target disease, may also require submission of additional scans/images/photographs eg, brain scan or photographs of cutaneous lesions. If a patient has had a tumour assessment that cannot be evaluated, then the patient will be assigned a visit response of not evaluable (unless there is evidence of progression, in which case the response will be assigned as disease progression). Endpoints ORR, DoR, BOR, TTR, and PFS will then be derived from the scan dates and overall visit responses.

The discordance between investigator assessment and BICR evaluation of measurable disease at baseline will be monitored. If the discordance is high (eg, > 5%), eligibility criteria may be amended to require measurable disease by BICR at baseline.

Further details of the BICR will be documented in an Independent Review Charter.

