9.4.2.1.2 Objective Response Rate

Determination of ORR by BICR is the primary objective, and as a sensitivity analysis, ORR by investigator recorded assessments will also be evaluated. Objective response rate is defined

as the proportion of patients who have a CR or PR prior to any evidence of progression (as defined by RECIST 1.1) that is confirmed at least 4 weeks later. The primary analysis of objective response rate will be based upon the safety analysis set. A sensitivity analysis will also be provided in the subset of patients in the safety analysis set who also have measurable disease at baseline by BICR. Data obtained from randomisation up until progression, or the last evaluable assessment in the absence of progression, will be included in the assessment of ORR, regardless of whether the patient withdraws from therapy. Patients who discontinue treatment without a response or progression, receive a subsequent therapy, and then respond will not be included as responders in the ORR.

As primary analysis, ORR will be summarised for each treatment arm non-comparatively with 95% CI (Clopper-Pearson).

As a secondary objective, ORR will be compared between the treatment arms using logistic regression adjusting for PD-(L)1 resistance type and LDH per randomisation stratification as covariates. The results of the analysis will be presented in terms of an odds ratio for study treatments together with associated 95% profile likelihood CI and p-value (based on twice the change in in log-likelihood resulting from the addition of a treatment factor to the model). This comparative analysis will be provided using the full analysis set.

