lymph nodes coalesce and are no longer individually separable within a conglomerate mass, the vector of the longest diameter of the coalesced mass should be used to determine the perpendicular vector for the maximal short axis diameter.

- If a TL is believed to be present and is faintly seen but too small to measure, a default value of 5 mm should be assigned. If an accurate measure can be given, this should be recorded, even if it is below 5 mm.
- If a TL cannot be measured accurately due to it being too large, provide an estimate of the size of the lesion. The choice of "Too large to measure" in the CRF will trigger an overall visit response of PD.
- When a TL has had any intervention (eg, definitive radiotherapy, embolisation, surgery, transarterial chemoembolisation, etc) during the study, the size of the TL should still be provided where possible and the intervention recorded in the RECIST 1.1 CRF for the current imaging visit and all subsequent visits. If a TL has been completely removed (surgery) or disappears, the longest diameter should be recorded as 0 mm.

Table 17 RECIST 1.1 Evaluation of Target Lesions

CR	Disappearance of all TLs since baseline. Any pathological lymph nodes selected as TLs must have a reduction in short axis diameter to < 10 mm.
PR	At least a 30% decrease in the sum of the diameters of TL, taking as reference the baseline sum of diameters.
SD	Neither sufficient decrease in the sum of diameters to qualify for PR nor sufficient increase to qualify for PD.
PD	At least a 20% increase in the sum of diameters of TLs, taking as reference the smallest previous sum of diameters (nadir). This includes the baseline sum if that is the smallest on study. In addition to the relative increase of 20%, the sum must demonstrate an absolute increase of at least 5 mm from nadir.
NE	Only relevant if any of the TLs at follow-up were not assessed or NE (eg, missing anatomy) or had a lesion intervention at this visit. Note: If the sum of diameters meets the PD criteria, PD overrides NE as a TL response.
Not applicable	Only relevant if no TLs present at baseline.

CR, complete response; NE, not evaluable; PD, progression of disease; PR, partial response; SD, stable disease; TL, target lesion.

RECIST 1.1 NTL assessment at follow-up

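### The Week 16 tumour-size measure has no cut-off at subsequent anti-cancer therapy, unlike best percentage change in the same section, so a few early switchers may be scored on their next treatment

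*Protocol*

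**What the plan says.** Section 9.4.2.2.5, and Table 5 in near-identical words, define the Week 16 value as the change in the sum of target lesions from baseline to Week 16, divided by the baseline sum, times 100, by BICR. The only exception is for early progressors. The text first says "Patients who progress before week 16 should have had a tumour assessment performed at the time of progression prior to treatment discontinuation", and then "The tumour size from their latest progression assessment will be used instead of the week 16 assessment for these patients". Subsequent therapy is not mentioned.

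A paragraph later, best percentage change uses assessments before the earliest of death without progression, "any evidence of progression, the start of subsequent anti-cancer therapy or the last evaluable RECIST assessment".

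Other parts of the protocol bear on this:

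- **ORR (section 9.4.2.1.2):** "Patients who discontinue treatment without a response or progression, receive a subsequent therapy, and then respond will not be included as responders in the ORR". Table 5 has a matching exclusion for TTR.
- **Follow-up (section 7.1.2):** patients who stop before RECIST progression are scanned "until RECIST 1.1 defined disease progression or death regardless of whether or not the patient started a subsequent anti-cancer therapy". Section 8.1.1 keeps the 8-weekly schedule irrespective of treatment decisions.
- **Investigator-based derivation (section 9.4.2.1.1.1):** all assessments enter the calculations. "This is also regardless of whether a patient discontinues study treatment or receives another anti-cancer therapy". Change in tumour size is among the endpoints listed there.
- **Output:** per-patient waterfall and spider plots. No test is planned for this endpoint.

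**The concern.** Two measures of the same quantity, defined in one section and plotted for the same patients, use different assessment windows. Best percentage change describes the patient up to the switch of therapy. The Week 16 change describes whatever the Week 16 scan shows, including shrinkage under the next treatment.

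Week 16 change is a named secondary measure, and the main study exists to estimate activity in each arm. A bar that reflects another drug misstates that patient's result. The Week 16 and best-change waterfalls can also contradict each other for one person. If early switching differs between the arms, the distortion differs too.

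**Working it through.** The protocol states no figure for this endpoint, so there is none to reproduce. The check has three steps.

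**1. Can a post-switch scan become the Week 16 value?**

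- Section 7.1 lets patients stop study treatment without RECIST progression, for example for an adverse event, by their own decision, or for clinical progression.
- Section 7.1.2 then continues tumour assessments "regardless of whether or not the patient started a subsequent anti-cancer therapy".
- With scans every 8 weeks, a switch between Weeks 8 and 16 leaves a Week 16 scan taken under the new therapy.
- The Week 16 rule takes that scan, because its one exception needs progression before Week 16.

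For investigator data, section 9.4.2.1.1.1 includes such scans explicitly. That covers the sensitivity analysis in Table 5 and, through Table 6, the biopsy sub-study. The BICR text states no cut-off in either direction.

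**2. Are the two rules coherent?** Take an assumed patient and the protocol's formula, 100 × (post − baseline) / baseline.

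| Assessment | Sum of target lesions | Change |
|---|---|---|
| Baseline | 100 mm | – |
| Week 8, on study treatment | 110 mm | 100 × (110 − 100)/100 = +10% |
| Week 16, on next therapy | 60 mm | 100 × (60 − 100)/100 = −40% |

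The Week 8 increase of 10% is below the 20% needed for target-lesion progression in Table 17, so the early-progressor exception does not apply. The patient stops for an adverse event and switches.

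- Week 16 value as written: −40%.
- Best percentage change, cut at the switch: +10%.
- Week 16 value with the same cut-off: +10%.

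A Week 16 value better than the patient's own best value is impossible if both measures use one window. Here it follows directly from the text.

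**3. How many bars could be affected?** The protocol gives no switching rate, so all inputs here are assumptions. Let f be the fraction who switch before Week 16 without progression, and p the fraction of those with at least 30% shrinkage at Week 16 on the next therapy. Expected spurious bars at or below −30% per 100 patients = 100 × f × p.

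| p | Basis | f = 3% | f = 10% |
|---|---|---|---|
| 4% | lower chemotherapy ORR cited in section 9.2.1, as a rough proxy | 0.12 | 0.4 |
| 10% | higher chemotherapy ORR cited there | 0.3 | 1.0 |
| 30% | assumed, more active next therapy | 0.9 | 3 |
| 60% | assumed, upper end | 1.8 | 6 |

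Per 100 patients the range is about 0.1 to 6. For the 50-patient arm it halves, to about 0.06 to 3. Only the conflict in step 2 is independent of these assumptions.

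**The case against.** Several stronger readings are tempting, and the protocol does not support them.

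- **That early progressors are credited with their next treatment.** They are not. The sentence before the substitution places their scan at progression and before study treatment stops.
- **That patients with investigator progression not confirmed by BICR are a main route.** The Synopsis ties continued scanning to absence of progression per investigator assessment, which largely closes it. Only a requested additional or follow-up scan (section 8.1.1, Appendix G) leaves a small opening.
- **That a resected target lesion simply counts as complete shrinkage.** Appendix G does say "If a TL has been completely removed (surgery) or disappears, the longest diameter should be recorded as 0 mm", but it also requires the intervention to be recorded, and Table 17 makes the target-lesion response not evaluable. Appendix G also governs investigator assessment, whereas the main Week 16 measure is by BICR.
- **That switchers become responders, or that arm means are biased.** ORR excludes responses that first appear after a new therapy, and no mean is planned for this endpoint.
- **That the authors clearly intended an on-treatment measure throughout.** DoR and PFS deliberately keep post-switch data, so handling is endpoint-specific and intent for Week 16 cannot be read off.

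Two further objections carry some weight. Clinical progressors might fall under the substitution, since section 9.4.2.2.5 says only that patients progress. The PFS text separates clinical from RECIST progression, so this is arguable either way. Magnitude is also limited: section 2.2.2 describes the available options as giving minimal benefit, so large post-switch shrinkage may be uncommon. Patients eligible for targeted therapy might do better, but no rate is given.

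Finally, landmark-visit derivations often belong in the SAP, which is not at hand and may add a cut-off. That does not dispose of the point. The protocol writes out a complete rule with one exception, then a different window for the companion measure, and the two give an incoherent result as they stand.

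**Conclusion.** The inconsistency is real, and its severity is minor. As written, a patient who stops without RECIST progression, starts another therapy before Week 16 and is scanned at Week 16 is scored on that therapy's effect. The clear cases are stopping for an adverse event or by choice; clinical progression is arguable.

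For such a patient the error can be tens of points (50 in the assumed record). How many there are is unknown from the protocol. The illustrative range of about 0.1 to 6 spurious bars per 100 rests wholly on assumed switching and shrinkage rates, and figures near its lower end fit the chemotherapy response rates the protocol cites. The consequence is confined to descriptive plots of a secondary endpoint. The primary ORR analysis and the planned comparisons are untouched.

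**What to change.** In section 9.4.2.2.5 and Table 5, add three statements:

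1. Only assessments before the start of subsequent anti-cancer therapy contribute to the Week 16 value.
2. Patients who start such therapy before Week 16 without progression use their last evaluable post-baseline assessment before it.
3. Patients with no such assessment, for example those who switch before the Week 8 scan, are treated as missing, and their number is reported by arm.

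It would help to say at the same time whether clinical progression without RECIST progression falls under the early-progressor substitution. The general inclusion sentence in section 9.4.2.1.1.1 should give way to endpoint-specific cut-offs.

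This extends to Week 16 the cut-off already written for best percentage change. The cost is a short text edit and one programming condition, with no change to visits, treatment or data collection. The downside is that a few Week 16 values become less favourable or missing.

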Objectives Endpoints To estimate the effectiveness of ceralasertib Time to response is defined as the time from monotherapy and ceralasertib plus durvalumab randomisation until the date of first documented by assessment of time to objective response objective response, which is subsequently (TTR) in patients with unresectable or advanced confirmed per RECIST 1.1 as assessed by melanoma and primary or secondary resistance BICR. The analysis will include all dosed to a PD-(L)1 inhibitor patients as dosed who have a confirmed response. Data obtained from randomisation up until progression, or the last evaluable assessment in the absence of progression, will be included in the assessment of TTR. Patients who go off treatment without a response or progression, receive a subsequent therapy, and then respond will not be included. The measure of interest is the median TTR and the proportion of patients with response at the first scheduled tumour assessment. Additionally, TTR will be analysed using the investigator assessment per RECIST 1.1 as a sensitivity analysis. To estimate the effectiveness of ceralasertib Percentage change from baseline in TL tumour monotherapy and ceralasertib plus durvalumab size is based on the RECIST 1.1 TL by assessment of change in target lesion (TL) measurements as assessed by BICR tumour size in patients with unresectable or Tumour size is the sum of the longest diameters of advanced melanoma and primary or secondary the TLs. The percentage change from baseline in TL resistance to a PD-(L)1 inhibitor tumour size at post-baseline assessment (week 16) is obtained for each patient taking the difference between the sum of the TLs at post-baseline assessment and the sum of the TLs at baseline divided by the sum of the TLs at baseline times 100. Patients who progress before week 16 should have had a tumour assessment performed at the time of progression prior to study treatment discontinuation. The tumour size from their latest progression assessment will be used instead of the week 16 assessment for these patients. The analysis will include all dosed patients as dosed. Additionally, best percentage changes from baseline in TL tumour size will be derived. Change in TL tumour size will also be analysed using the investigator assessment per RECIST 1.1 as a sensitivity analysis.

Objectives	Endpoints

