8.1 Efficacy Assessments

8.1.1 Tumour Assessments

Tumour response will be evaluated by the investigator and by BICR (main study only) according to RECIST 1.1. All treatment decisions will be based on on-site assessment of scans. Patients who are determined to have progressed according to RECIST 1.1 criteria by the investigator will have scans centrally reviewed for confirmation of objective disease progression. If disease progression is not confirmed at central review an additional RECIST 1.1 assessment may be requested preferably at the next scheduled RECIST 1.1 visit.

Baseline tumour assessments should encompass all areas of known predilection for metastases in the disease under evaluation and should additionally investigate areas that may be involved based on signs and symptoms of individual patients. Baseline assessments should be performed no more than 21 days before randomisation, and ideally should be performed as close as possible to the start of study treatment. The methods of assessment used at baseline should be used at each subsequent follow-up assessment.

Tumour assessment will be conducted every 8 weeks (± 1 week) after the start of treatment (Cycle 1 Day 1) up to 18 months, then every 12 weeks (± 1 week) until objective disease progression as per RECIST 1.1, irrespective of treatment decisions. In the event of treatment interruptions or delays, tumour assessments should proceed to schedule relative to Cycle 1 Day 1. Tumour assessments (RECIST 1.1) are to continue according to schedule in patients who discontinue treatment for reasons other than disease progression.

Any other sites at which new disease is suspected should also be appropriately imaged. If an unscheduled assessment is performed (eg, to investigate clinical signs and symptoms of progression) and the patient has not progressed, every attempt should be made to perform subsequent assessments at the scheduled visits whilst the patient remains on study treatment.

Digital colour photographs documenting measurable lesions including a ruler to estimate the size of the lesion, should be obtained if the cutaneous lesion is included as part of the non-target lesions for disease assessment according to RECIST 1.1. Copies of the photograph should be forwarded to the central imaging vendor for potential retrospective analysis. The timing for capturing cutaneous lesion photographs should follow the same schedule as the imaging scans.

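### Read literally, the best percentage change rule in Section 9.4.2.2.5 leaves first-scan progressors and single-scan patients without a value and drops the latest scan of ongoing patients

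*Protocol*

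**What the plan says.** Table 5 in Section 3 makes change in target-lesion size a secondary endpoint. Beside the Week 16 change it states that "best percentage changes from baseline in TL tumour size will be derived". On the population for this endpoint it says "The analysis will include all dosed patients as dosed".

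Section 9.4.2.2.5 defines best change as "the largest decrease from baseline or the smallest increase from baseline in the absence of a reduction". It then sets the window: the derivation "will include all assessments prior to the earliest of death in the absence of progression, any evidence of progression". Two more cut-offs complete the list. One is a switch to another cancer treatment. The final one covers patients with none of these events and reads "or the last evaluable RECIST assessment if the patient has not died, progressed or started subsequent anti-cancer therapy". The words *prior to* govern every item in that list.

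For the Week 16 change, the same section treats patients who progress before Week 16 in another way: "The tumour size from their latest progression assessment will be used instead of the week 16 assessment for these patients".

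Both measures are to be plotted. The section says that "best percentage change in tumour size will be presented visually for each patient by waterfall and spider plots".

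On timing, Section 8.1.1 says "Tumour assessment will be conducted every 8 weeks (± 1 week) after the start of treatment", so the first post-baseline scan falls at about Week 8.

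**The concern.** A window that closes before the first evidence of progression contains no post-baseline scan for a patient who progresses at Week 8. Later scans cannot fill the gap, because they also lie beyond the cut-off, and no fallback is given. Best change is then undefined for some of the patients with the worst outcomes.

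The same *prior to* reaches the last evaluable assessment. A patient still in follow-up without progression would lose the most recent scan, and one with a single scan so far would have no value.

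At stake is the best-change waterfall, which readers use to judge depth of response. If early progressors have no bar, the remaining bars look better than the treated population did. Tumour size is also listed as an interim output in Table 16, so the same rule could shape what the data monitoring committee sees. Finally, two programmers working from this text could produce different plots, one following the words and the other the apparent intent.

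**Working it through.** The plan states no figure on this point, so there is none to reproduce. The check applies the rule to example patients, compares it with the neighbouring text, and then sizes the effect under a stated assumption.

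**Step 1. The rule on example patients.** Each entry is the percentage change in target-lesion sum per scan. *Strict* excludes the cut-off scan; *inclusive* keeps it.

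| Patient | Strict | Inclusive |
|---|---|---|
| Progression at scan 1, +45% | no value | +45% |
| Progression at scan 1 by new lesion, target lesions −10% | no value | −10% |
| Stable +8%, then progression +30% | +8% | +8% |
| Partial response −40%, then progression −15% | −40% | −40% |
| No progression, one scan, −20% | no value | −20% |
| No progression, −20% then −35% | −20% | −35% |

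The two readings differ for first-scan progressors, single-scan patients and ongoing patients whose latest scan is their best. In the two examples with an earlier scan before progression, they agree.

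**Step 2. Comparison with the rest of the plan.**

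- *Plot for each patient* (Section 9.4.2.2.5): the strict reading cannot deliver this for rows 1, 2 and 5.
- *All dosed patients* (Table 5): same conflict. Dosed patients with no post-baseline scan have no value under either reading.
- *Week 16 rule* (same section): it uses the progression assessment for patients who progress before Week 16, so rows 1 and 2 have a Week 16 value but no best-change value.

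**Step 3. Size, under an assumption.**

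Inputs: planned arm sizes of about 100 and 50 (Section 4.1). The protocol gives no rate of progression at the first scan. The nearest figure is the disease control rate of 63.3% in the single-centre combination study of 30 patients (Sections 4.2 and 4.3.2).

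Check of that figure: 19/30 = 0.633. The Wald interval is 0.633 ± 1.96 × √(0.633 × 0.367 / 30) = 0.633 ± 0.172, or 46.1% to 80.6%, which agrees with Section 4.3.2.

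The complement, 1 − 19/30 = 11/30 = 36.7%, serves as the upper end of the assumed range; 20% is an assumed lower end.

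- Combination arm: 100 × 0.20 = 20; 100 × 0.367 = 36.7, about 37.
- Monotherapy arm: 50 × 0.20 = 10; 50 × 0.367 = 18.3, about 18.

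These count only first-scan progressors. Single-scan patients without progression would add to them.

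**The case against.** The strongest reply is that nobody means the strict reading. It would discard the last scan of every ongoing patient, which is absurd, and the same section promises a plot for each patient. On this view *prior to* is loose drafting for *up to*, and any sensible programmer would read it so. The point about likely intent stands: a reader might infer that the plan deliberately excludes early progressors, and the text does not support that. What does not follow is that the wording can stay. A derivation rule that works only when read against its own words should be corrected.

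A second reply is that Section 9.4 is a summary and the detail belongs to the SAP. That would answer a missing detail. Here the protocol states a specific rule, and a SAP that copied it would carry the fault while one that departed from it would contradict the protocol.

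Third, the consequences are limited, and this stands in full. A reader might infer that early progressors disappear from the waterfall plots altogether. They do not: the Week 16 plot keeps them through their progression scan, and change is calculated at each visit. A reader might also infer a biased comparison between arms, but no between-arm test of tumour size is planned and the display is visual.

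Fourth, the direction of the effect is not fixed. Losing the last scan of ongoing patients can hide their deepest shrinkage, and single-scan patients with shrinkage would drop out too. A first-scan progressor may also have shrinking target lesions if progression came from a new or non-target lesion. These losses work against a flattering picture, so the net effect is a tendency.

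Fifth, the disease control figure is a weak proxy. The documents do not define it for that study, so its complement may include later progression or patients who could not be evaluated. That study was small, gave only the combination, and used Days 15 to 28 for ceralasertib rather than Days 1 to 7. This also stands, and is why the counts are labelled an assumption.

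**Conclusion.** The point holds as a wording fault in a stated derivation rule for part of a secondary endpoint. Taken literally, Section 9.4.2.2.5 gives no best percentage change to first-scan progressors and single-scan patients and drops the latest scan of ongoing patients, against the plan's own statements on population, plots and Week 16 handling.

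If the rule is programmed as written, the best-change waterfall would tend to look too favourable, with a partial offset of unknown size. If 20% to 37% progress at the first scan, about 20 to 37 of 100 and 10 to 18 of 50 patients would lack a value. The true number is unknown. It is tempting to go further and state by how much the share of patients with shrinkage would be overstated. That would need a shrinkage rate, which the protocol does not give, and the assumption that no first-scan progressor had shrinking target lesions.

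The primary ORR analysis, PFS and OS do not use this rule and are unaffected.

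**What to change.** In Section 9.4.2.2.5, replace the phrase that opens the window with: *up to and including the first assessment showing progression, or the last evaluable assessment in the absence of progression, and before the start of subsequent anti-cancer therapy*. Make the same change in the SAP wherever it repeats the rule. It would help to show, beside the plot, how many dosed patients per arm have no post-baseline target-lesion measurement, since they are missing under any wording.

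The cost is one phrase and a check of the derivation program. The scans are already collected, and no sample size, test or schedule changes.
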